4.2 Secondary Objectives

Our secondary objectives are:

- (i) To assess if unexpected death of a simulated patient is associated with an impaired retention of technical resuscitation skills.
- (ii) To examine if unexpected death of a simulated patient is associated with future higher stress levels and stronger emotions during simulated crisis.
- (iii) To investigate the relationship between stress levels as well as emotions and future performance in crisis.

We furthermore hypothesize, that simulated death will lead to higher stress levels as well as more negative emotions and will thereby impact the ability to retain critical skills.

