6.1.4 Emotion Assessment

Emotions are inevitably linked to the occurrence of expected and unexpected death while treating a patient or patient simulator.¹⁶ As these feelings may foster or impair the learning effect, emotions that occurred throughout the simulation scenarios will be assessed. Participants will be asked to classify their emotions they experienced throughout the study by using the established Positive and Negative Affect Schedule (PANAS) at the end of each scenario. This assessment will be done immediately after debriefing of the respective scenarios.

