7.1.2 Secondary outcome parameters

Secondary outcomes will be (i) technical resuscitation skills (performance and retention) measured by the American Heart Association's Megacode Checklist (ii) stress including salivary cortisol, cognitive appraisal and STAI and (iii) valence of emotions.

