Impact of Unexpected Death in Simulation: Skill Retention, Stress and Emotions

Data Analysis Plan

Primary Outcome: Difference in retention of non-technical crisis resource management (CRM) skills using Ottawa Global Rating Scale (OGRS)

ANCOVA:

- Dependent variable: OGRS score (total score)
- Independent variable: Death vs. survival
- Covariates: Junior vs. senior; Acute vs. non-acute

Secondary Outcome 1: Technical CRM skills (according to checklist)

- Same Videos to be provided for primary outcome will be scored using the “Task-specific checklist” (derived from American Heart Association’s Megacode Checklist) and given a score out of 18

ANCOVA:

- Dependent variable: Task-specific checklist score (total score)
- Independent variable: Death vs. survival
- Covariates: Junior vs. senior; Acute vs. non-acute

Secondary Outcome 2: Stress

Measure 1: Salivary cortisol

Five time points (minutes passed since baseline):

1. Baseline (0 minutes) during the accommodation period at the beginning of the day
2. Before scenario (10 minutes)
3. Immediately after scenario (30 minutes)
4. 30 minutes after start of scenario (45 minutes)
5. After debrief (50 minutes)

ANCOVA:

- Dependent variable: Change in cortisol concentration (versus baseline) at a given time point (for each time point)
- Independent variable: Death vs. survival
- Covariates: Junior vs. senior; Acute vs. non-acute

Regression:

- Linear regression to determine the effects of covariates (Junior vs. senior; Acute vs. non-acute) on change in cortisol concentration over time
 - Separated into “death” and “survival” groups
 - Change in cortisol concentration will be established using the baseline reading of each participant on each day of the study (time point 1).
- Unpaired t-tests will be used to compare change in cortisol levels between the “death” group and the “survival” group at each time point.

Measure 2: State-Trait Anxiety Inventory (STAI)

- Analysis will be carried out in the same way as the cortisol measures with the STAI score taking the place of the change in cortisol concentration

Measure 3: Cognitive appraisal

- Mean cognitive appraisal ratios for each group (“death” and “survival”) at each time point will be calculated and subjected to a one-sample t-test to determine whether they are significantly different from 1.
- Unpaired t-tests will be used to compare the mean ratios of the “death” and “survival” groups at each time point.

Secondary Outcome 3: Valence of emotions

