Five-point Likert scale

Repeated measures ANCOVA:

- Dependent variable: Score for each emotion
- Independent variable: Death vs. survival
- Covariates: Junior vs. senior; Acute vs. non-acute
- Time points: Initial and retention

For all Outcomes:

Relationships between all outcomes (determined by ANCOVA or by Pearson’s correlation) will be presented in a matrix table.

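### The emotion outcome is valence, but the SAP models each emotion separately and defines neither an affect score nor the session contrast to be tested

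*SAP*

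**What the plan says.** Protocol 7.1.2 lists "valence of emotions" as the third secondary outcome. Protocol 4.2 closes with the hypothesis that "simulated death will lead to higher stress levels as well as more negative emotions". Objective (ii) in the same section has no direction: it asks whether death is "associated with future higher stress levels and stronger emotions during simulated crisis". Protocol 6.1.4 measures emotions "by using the established Positive and Negative Affect Schedule (PANAS) at the end of each scenario" and gives no scoring rule.

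The SAP keeps valence in the title of Secondary Outcome 3, mentions a five-point Likert scale, and plans one repeated measures ANCOVA. Its specification is "Dependent variable: Score for each emotion", with death versus survival as the independent variable, the two stratification factors as covariates, and the initial and retention sessions as time points. It does not say which effect in this model is the test. For the OGRS and the technical checklist, by contrast, the SAP states that the total score is the dependent variable.

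Protocol 7.3 plans ANCOVA for the outcome parameters in general. Protocol 6, under Retention Test, switches the mannequin's outcome at three months, so each group meets one death and one survival.

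**The concern.** The hypothesis is about a direction: more negative affect. A list of separate emotion results does not give one answer to it. If a few negative emotions rise, one falls and the rest do not move, the plan has no rule for saying whether valence changed. A modest rise spread over all the negative emotions can be missed one at a time, while a single chance result can be reported as an emotional effect of death.

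The gap carries into other analyses. Objective (iii) relates emotions to later performance, Protocol 7.3 plans regressions of each outcome on emotions, and the SAP ends with a matrix of relationships among all outcomes. Each needs a defined emotion variable; with separate scores, each multiplies by the number of emotions.

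The unnamed time contrast adds to this. Because the outcome is switched at retention, a group effect averaged over both sessions does not compare death with survival.

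**Working it through.** **Inputs.** From the documents: two-sided 0.05, power 0.80, d = 0.8, r² = 0.12, 46 evaluable participants (Protocol 7.2) and 1:1 allocation (Protocol 6.2). Assumed, because the documents do not give them: k = 10 or 20 items, inter-item correlation r from 0.2 to 0.6, and a shift of 0.5 SD per item in the power example.

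**Plan's own figure.** A two-sample t-test at d = 0.8 needs 25.5, so 26 per arm or 52 in total. 52 × (1 − 0.12) = 45.8, so 46, or 23 per arm. This concerns the primary outcome. The documents give no power or error rate for emotions; 23 per arm is used below only as the evaluable size.

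**1. False positives, independent items.** The chance of at least one is 1 − 0.95^k.
- k = 10: 1 − 0.95^10 = 0.40
- k = 20: 1 − 0.95^20 = 0.64
- two scores: 1 − 0.95^2 = 0.0975
- one score: 0.05

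**2. False positives, correlated items.** Simulated t-tests with no true difference, 23 per arm, normal items with equal correlation, 3,000 trials per cell:

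| Items | r = 0.2 | r = 0.4 | r = 0.6 |
|---|---|---|---|
| 10 | 38% | 32% | 25% |
| 20 | 58% | 47% | 36% |

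The mean of the items rejected in 5.0% to 5.6% of trials.

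**3. Effect on a total.** The variance of a mean of k items, relative to one item, is (1 + (k − 1)r)/k. If all items shift equally, the standardised effect grows by the inverse of its square root. For k = 10:
- r = 0.2: 2.8/10 = 0.28, SD 0.53, factor 1.89
- r = 0.3: 3.7/10 = 0.37, SD 0.61, factor 1.64
- r = 0.6: 6.4/10 = 0.64, SD 0.80, factor 1.25

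If only m of the 10 items shift, the factor is multiplied by m/10. With m = 5 it becomes 0.95, 0.82 and 0.63, so the total then shows a smaller standardised effect than an affected item does.

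**4. Power.** Same simulation, all 10 negative items shifted by 0.5 SD:

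| Test | r = 0.2 | r = 0.4 | r = 0.6 |
|---|---|---|---|
| One given item | 38% | 38% | 38% |
| Any item, Bonferroni | 60% | 50% | 42% |
| Composite | 88% | 69% | 55% |

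Any item without adjustment reaches 95%, 89% and 79%, but at the error rates in step 2.

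**5. Session contrast.** Let death raise negative affect by δ in the session where it occurs, the same at either session, and let an earlier death leave a carry-over γ at retention.

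| | Initial | Retention | Mean |
|---|---|---|---|
| Death first | δ | γ | (δ + γ)/2 |
| Survival first | 0 | δ | δ/2 |
| Difference | δ | γ − δ | γ/2 |

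The immediate effect δ cancels from the averaged group effect. It appears alone only in the initial-session difference. The group-by-time contrast, initial minus retention, is 2δ − γ.

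**The case against.** Four points can be made for the plan.

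First, a reader might infer that no planned test answers the stated question. The documents do not support that. Protocol 7.3 nominally applies ANCOVA to every outcome parameter, valence included; tests of individual negative emotions bear on the hypothesis in part; and objective (ii), like the abstract, speaks of stronger emotions, which separate scores can address. All of this stands. Protocol 7.3 does not close the gap, however, because it defines no score for valence.

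Second, a reader might infer that the trial will be unable to say whether death made emotions more negative. That does not follow either. The PANAS is completed at both sessions, so totals can be formed from data already planned. The fault is in pre-specification, not data collection.

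Third, the SAP gives no item list, so each emotion could have been meant more broadly than each item. The mention of a five-point scale and the explicit total score for two other outcomes favour the item reading, but it remains a reading.

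Fourth, this is a third-ranked secondary outcome, and Protocol 8.2 calls every aspect of the study hypothesis-generating. Describing separate emotions is a legitimate exploratory choice, and if death moves only a few of them a total dilutes the effect, as step 3 shows. That supports keeping the single-emotion results, suitably labelled. It does not explain why the stated hypothesis has no score of its own.

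**Conclusion.** The concern holds in this form: the only specified emotion model uses separate emotion scores, while the outcome is valence and the hypothesis is more negative emotions. No affect score, combining rule, multiplicity adjustment or session contrast is defined.

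The size depends on assumptions. For 10 to 20 items, the chance of at least one false positive is 40% to 64% under independence and about 25% to 58% at correlations of 0.2 to 0.6, against 5% for one score. The independence figures are the upper end and should not be quoted beside a gain computed from correlated items. For 10 negative items that all shift equally, the standardised effect on the total is about 1.9, 1.6 or 1.25 times that on one item at correlations of 0.2, 0.3 or 0.6. That gain shrinks, and can reverse, if few emotions move.

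The session contrast needs no item count. Under the model in step 5, a group effect averaged over sessions does not isolate the effect of death, whichever score is used.

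**What to change.** In the SAP, under Secondary Outcome 3:

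- Make the negative-affect total the dependent variable for the hypothesis and the positive-affect total the second, each with group and both strata in the model. State how items form each total. If both totals are to carry formal claims, test each at 0.025, since two tests at 0.05 give 9.75% if independent.
- Name the between-group difference at the initial session as the contrast tested. Report the retention difference or the group-by-time contrast separately, noting that the switched outcome mixes carry-over with the ending just seen.
- Report single emotions descriptively or with a stated multiplicity adjustment.
- Use the same totals in the regressions and the relationship matrix.

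The cost is SAP wording and the loss of unadjusted formal tests of single emotions. No extra data or participants are needed.

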differ slightly in order to eliminate the potential for this recall bias described above. In summary, the scenarios are of equal complexity, but differ primarily with respect to the clinical context, initial cardiac arrest rhythm and pre-determined outcome (Appendix C).

Two well-trained confederates will act as registered nurse and as respiratory therapist within the team. These roles were prescribed to ensure standardization for each participant. The confederates will be instructed to help and to perform tasks when directed but not to offer crisis management advice or differential diagnoses. An individualized, video-assisted, instructor-led, structured debriefing lasting 30 minutes will follow the initial scenario. As suggested by Gaba, highly experienced and well prepared instructors will lead the debriefing phase in order to deal with potential upcoming emotions and issues.¹⁹ All scenarios and debriefings will be video recorded for performance analysis.

Retention Test

Previous data have shown that, even with high-fidelity simulation, resuscitation knowledge and skills deteriorate between as early as 2 weeks and 1 year after the learning intervention, with a faster decay in skill.^{21,22} Therefore a retention test is planned 3 months after the initial test. After a short accommodation phase of 15 minutes and assessment of baseline data a standardized scenario briefing will be done. Participants from both groups will be asked to be team-leader in a cardiac arrest scenario to test for skill retention. Again, two confederates, one acting as registered nurse and one acting as respiratory therapist will be team members. While the scenarios will be the same as in the initial test, the case presentation of the scenario and the mannequin “outcome” will be switched for the retention test. The mannequin will survive for the “unexpected death” group and it will die in the “survive” group. That way, each participant will be exposed to simulation death in the study once. To maximize learning opportunities for participants in this study, an individualized debriefing with a specially trained facilitator will follow the retention test as well.

All scenarios and debriefings will be video recorded for further performance analysis.

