Following the retention scenario and completion of risk assessment, participants will be interviewed to determine their subjective views of their decision-making and performance within an orally administered survey approximately 30 minutes in length.

Both Phases

The setting and equipment will be the same in the initial and the retention phase, reflecting an appropriately equipped normal ward room at our hospital. SimMan (Laerdal, Stavanger, Norway) will be used as the standardized simulation mannequin in all scenarios. The mannequin will be placed in a patient bed. The mannequin will be operated by an experienced simulation specialist from a separated control room. All scenarios will be peer reviewed and validated by experts in the field of medical simulation and resuscitation. The scenarios will be prescribed for a duration of maximum 15 minutes. The confederates acting as team members during the scenarios will receive extensive precourse training with prescribed responses and interactions. Predefined, peer reviewed cues will be given by the supporting staff in case the participants fail to recognize the cardiac arrest situation. These cues will include the repetition of the case presentation and vital parameters.

Each phase is accompanied by assessment of baseline data, stress parameters and emotions. All scenarios and debriefings will be video recorded to allow performance assessment by two independent experts raters blinded to group allocation.

In order to collect meaningful qualitative data from a maximum of subjects, all subjects will be exposed to unexpected death either during their initial or retention scenario. Subjects of group “unexpected death” will have their simulated patient survive during the retention test while subjects from the group “survive” will have their patient die during the retention scenario. The course of both

subsets of scenarios is the same up until the final two minutes, and the final outcome of the scenarios will not be seen by the expert raters. Therefore, we do not consider this trial as a crossover design.

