6.1.3 Stress Assessment

Acute stress will be assessed by means of salivary cortisol, the State-Trait Anxiety Inventory (STAI) and questionnaire aligned with the cognitive appraisal theory.^{4,5,10,25}

Salivary Cortisol

The activation of the hypothalamic-pituitary-adrenal axis as surrogate for psychological stress will be measured using salivary cortisol levels that show a close to linear relationship to plasma cortisol levels.^{4,5,26} Cortisol levels will be measured in both simulation tests (initial test and retention test). Salivary cortisol peaks at 20 to 40 minutes after the onset of a stressor.⁴ In order to approach cortisol kinetic, 5 cortisol samples will be obtained per participant per scenario: when participants arrive at the simulation center (sample 0), just before each scenario (sample 1), immediately at the end of the each scenario (sample 2), 30 minutes after the start of the scenario (sample 3), and at the end of the debriefing phase (sample 4). The cortisol sampling schedule for the initial and the retention test will be identically, resulting in a total of 10 cortisol samples per participants (see Appendix D). A roll shaped synthetic saliva collector (Salivette for Cortisol testing, Starstedt, Montreal, Quebec, Canada) will be used and will be frozen at -20°C until analysis using an ELISA technique at the Technische Universität Dresden, Germany.

State-Trait Anxiety Inventory (STAI)

To evaluate acute and subjective stress the standardized test battery of the STAI will be used. With STAI state anxiety at the very given moment can be measured using 20 statements to which the participants agree or disagree on a four point Likert-like scale (1 – not at all, 4 very much so). The sub scores are summed up and provide a sensitive basis for acute changes in anxiety related to stressful simulation.^{10,25} STAI will be assessed after the resting phase before each scenario and immediately after the debriefing of the initial and the retention scenario.

Cognitive Appraisal

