7.3 Statistical analysis

As it has been suggested as best practice for stratified randomized controlled trials, ANCOVA will be used to analyze the outcome parameters using the level of training (PGY1-3 vs PGY 4-5 and fellows) and specialities (acute care specialities vs. non-acute care specialities) as covariates.³⁵ Group assignment (unexpected death, alive) will be used as the independent variable. Demographic data will be analyzed using an unpaired Student's *t*-test or chi-square test, where appropriate.

Curved/linear regression analysis will be performed to assess the correlations between each outcome and stress as well as emotions. As it is common practice, results of Likert-like scales will be treated as interval-measures and thereby analyzed by using parametric tests.^{36,37}

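### Because the ending is switched at retention, the two-visit emotion ANCOVA cannot isolate a lasting effect of simulated death without an assumption that neither document states

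*SAP*

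**What the plan says.** Protocol section 6 (Retention Test) reverses the mannequin's outcome at the second visit: it survives for participants whose first patient died, and dies for the others. "That way, each participant will be exposed to simulation death in the study once". Under Both Phases the two versions are said to match except at the end ("subsets of scenarios is the same up until the final two minutes") and the raters do not see the ending. From this the protocol concludes: "Therefore, we do not consider this trial as a crossover design".

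Protocol section 4.2, objective (ii), is "To examine if unexpected death of a simulated patient is associated with future higher stress levels and stronger emotions during simulated crisis".

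Timing of the self-reports and cortisol:
- PANAS (section 6.1.4) is completed after each scenario's debriefing, so always after the ending. There is no pre-scenario PANAS.
- "STAI will be assessed after the resting phase before each scenario and immediately after the debriefing of the initial and the retention scenario" (section 6.1.3).
- Appraisal is asked after the briefing and again after the scenario.
- Cortisol has five samples per visit. The SAP analyses them as change from that day's baseline.

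For the analysis, protocol section 7.3 says "Group assignment (unexpected death, alive) will be used as the independent variable". The SAP's emotion analysis is a repeated measures ANCOVA on death versus survival with two strata as covariates and "Time points: Initial and retention". It does not say whether the group effect, group-by-time or a per-visit contrast is the test.

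**The concern.** Objective (ii) is about the future: does a simulated death change stress and emotions in a later crisis? At that later crisis the control group has just seen its own patient die, so no group at retention is free of death. Any emotion score taken there mixes what remains of the first death with the fresh effect of the second.

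This can mislead in two directions. A pooled or retention contrast near zero could be reported as no effect of death when two real effects have cancelled. A non-zero pooled effect could be reported as lasting when death merely had a weaker immediate effect the second time. With no test term named, the term could be chosen after the results are known.

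**Working it through.** **Inputs.** Evaluable sample 46, or 23 per group, and 56 recruited, or 28 per group (protocol 7.2). Two-sided 0.05 and an effect of 0.8 SD (7.2; a design figure, not one for emotions). Within-person correlation r is in neither document, so 0.3, 0.5 and 0.7 are assumed. Neither document gives a figure for the emotion analysis. The 46 itself reproduces: a two-sample t-test at 0.8 SD and 80% power needs 52, and 52 × (1 − 0.12) = 45.76.

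**Cell means after the ending**, in SD units relative to each visit's mean without death:

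| Group | Initial | Retention |
|---|---|---|
| Death first | d1 | L |
| Survive first | 0 | d2 |

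**Contrasts, with randomised group as the factor:**
- Initial visit: d1
- Retention: L − d2
- Pooled over visits: (d1 + L − d2)/2
- Group-by-time: d1 − (L − d2) = d1 + d2 − L

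Four cell means carry five unknowns (two visit means, d1, d2, L), and the design matrix has rank 4. So d1 and L − d2 can be estimated, but L and d2 cannot be separated. An outside assumption restores L. If d2 = d1, L is twice the pooled effect. If d2 is negligible, the retention contrast is L. A known value of d2, or of the ratio d2/d1, would also serve.

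**Rejection rates.** Noncentral t, 23 per group, 44 df, no covariates. The SD of a single visit is 1, of the visit mean √((1 + r)/2), and of the visit difference √(2(1 − r)). Ranges run over r = 0.3 to 0.7.

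| d1, d2, L | Pooled | Rejects | Retention | Rejects | Group-by-time | Rejects |
|---|---|---|---|---|---|---|
| 0.8, 0.8, 0 | 0.0 | 5% | −0.8 | 76% | 1.6 | over 99% |
| 0.8, 0.8, 0.4 | 0.2 | 11–13% | −0.4 | 26% | 1.2 | 92% to over 99% |
| 0.8, 0.4, 0 | 0.2 | 11–13% | −0.4 | 26% | 1.2 | 92% to over 99% |
| 0.8, 0.2, 0 | 0.3 | 19–24% | −0.2 | 10% | 1.0 | 80–99% |
| 0.8, 0, 0 | 0.4 | 30–38% | 0.0 | 5% | 0.8 | 61–93% |
| 0.8, 0.8, 0.8 | 0.4 | 30–38% | 0.0 | 5% | 0.8 | 61–93% |

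Rows two and three are the key pair. One has a lasting effect and the other has none, yet every contrast is identical. The last two rows make the same point: L is 0 in one and 0.8 in the other. Row one shows that a significant group-by-time term is compatible with L = 0.

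For comparison, the initial-visit contrast at d1 = 0.8 has 76% power with 23 per group and 84% with 28. A retention measure taken before the ending would have 76% for L = 0.8.

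**Which stress measures share the problem.** Post-debrief STAI and post-scenario appraisal at retention follow the ending, so they estimate L − d2. For cortisol, take a 15-minute scenario that diverges at minute 13:
- Sample 2 is at minute 15, 2 minutes after divergence.
- Sample 3 is at minute 30, 17 minutes after.
- Sample 4 is at minute 35 on the SAP clock (50 − 15) or minute 45 with a 30-minute debriefing, so 22 to 32 minutes after.

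The protocol states "Salivary cortisol peaks at 20 to 40 minutes after the onset of a stressor". Sample 4 is therefore exposed to the ending, sample 3 may be partly exposed, and sample 2 is little affected but precedes the peak from scenario onset. Samples 0 and 1, pre-scenario STAI and pre-scenario appraisal all precede the ending.

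**The case against.** **Coding.** A reader might infer that the SAP leaves open whether death versus survival means randomised group or that day's outcome. Protocol 7.3 names group assignment, and the SAP speaks of death and survival groups, so the coding is largely settled as randomised group. Only the test term is missing.

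**The assumption.** A reader might infer that d1 = d2 is the only way to recover L. It is not: a negligible d2 would make the retention contrast L itself. Protocol 6.4.2 leans that way, reporting that in earlier stressful simulations stress returned to baseline by the end of the scenario and that residual negative feelings concerned participants' own performance. But the same section says death may aggravate stress and emotions, and the trial's hypothesis is that it does. No passage states an assumption about d2.

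**The interaction.** A conventional repeated measures analysis would report group-by-time, which is powerful for an immediate effect. That stands, so it would be wrong to say that the plan would probably miss the effect of death altogether. The term still does not answer objective (ii).

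**Size of the illustrations.** The 0.8 SD is not an emotion figure, exact cancellation is a special case, and the covariates are left out. Applying the r² of 0.12 from section 7.2 to emotions would raise the initial-visit power from 76–84% to about 81–88%. The rank result depends on none of these values.

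**Deliberate design.** Section 6 explains the switch as a way to obtain qualitative data from as many participants as possible, and section 8.2 calls all findings hypothesis-generating. Both are fair, but neither mentions this confounding. The reason given for denying a crossover covers what raters see; participants do see the ending.

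**Conclusion.** The point holds for the emotion outcome and for retention stress measures taken after the ending. By algebra alone, no emotion contrast isolates the lasting effect without an outside assumption about d2, and the documents state none. If the pooled effect were used, a large immediate effect could cancel to a 5% rejection rate, or a false lasting effect could appear in 19–24% of trials (d2 = 0.2) and up to 38% (d2 = 0). These rates assume 23 per group, 0.8 SD and r of 0.3 to 0.7.

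A reader might extend this to the whole trial, but the documents do not support that. The primary and checklist outcomes are rated from video that omits the ending, initial-visit contrasts estimate d1 cleanly, and pre-scenario STAI and appraisal at retention, which the SAP already plans to test, precede the second ending. The broader hypothesis that death raises stress and negative emotions can be answered from the initial visit. This is a cheap improvement to secondary outcomes only.

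**What to change.** 1. In SAP Secondary Outcome 3, take the immediate effect of death on emotions from the initial-visit PANAS contrast by randomised group, adjusted for the two strata, in everyone tested at that visit. Do not use the effect pooled over visits for this. If group-by-time is reported, say that it estimates d1 + d2 − L.
2. For a lasting effect on stress, use retention measures taken before the ending: pre-scenario STAI, pre-scenario appraisal, and cortisol samples 0 and 1. Analyse those two samples as raw values as well, because change from same-day baseline removes any elevation already present on arrival.
3. Label retention PANAS, and the other retention measures taken after the ending, as estimating L − d2. If any of them, or the pooled effect, is read as a lasting effect, state the assumption about d2 on which that reading rests.
4. In protocol section 6, limit the statement that this is not a crossover to video-rated performance.

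The cost is wording in the SAP and protocol; every measure is already collected. The downside is that the stress part of objective (ii) becomes mainly anticipatory, since these measures precede the crisis, and its emotion part remains conditional on a stated assumption.
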